Clinicaltrials.gov: Cover page

Official title of study:

Improving Chronic Illness Management With the Apsaalooke Nation: The Baa
Nnilah Project

NCT number: NCT03036189

Date of the document: 8/23/22

Statistical Analysis Plan

Statistical analysis. Statistical analyses were conducted using SAS 9.4®.³¹ Descriptive statistics were obtained for all study variables. Mean and standard deviation were calculated for continuous variables, and frequency and percentage for categorical variables. Distributions of continuous variables were examined for non-normality and outliers. Missing data patterns were examined for all variables. To compare the two study groups on baseline demographic characteristics and outcome measures, independent *t*-tests were conducted for the continuous variables, and chi-square tests for the categorical variables.

To test the main hypotheses regarding the effectiveness of the intervention and longitudinal trend on each outcome measure, a hierarchical linear modeling (HLM) approach was adopted, and each hypothesis was tested in SAS 9.4 using the *Proc Mixed* procedure. Observations were nested within individuals and individuals nested within family/clan clusters. Up to four observations (i.e., measurements over four waves of data collection) per participant in the intervention group ($n = 104$, number of clusters = 45) and up to five observations per participant in the WLC group ($n = 107$, number of clusters = 50) were obtained. All available observations were included in the analysis to test whether the outcome measure changed significantly over time (i.e., number of weeks since baseline) and whether the change significantly differed between the two study groups.) Time-invariant covariates included age at baseline, sex, study group membership, number of chronic illnesses, and number of gatherings attended. In addition, a dummy variable indicating whether each participant had attended intervention sessions at each time of data collection was included in the analytical model as a time-varying covariate. The number of valid data points varied across individuals, as well as by time and by variable within each individual, because participants could 1) miss a data collection but complete subsequent data collection(s) and/or 2) choose not to complete a physical test or a survey question. Full information maximum likelihood estimation (MLE) was used to handle missing data, which allowed us to use all available non-missing data.

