Aim 2: Test the effects of the *Baa nnilah* intervention versus usual care using a wait-list control group effectiveness trial among 200 randomly assigned AI men and women 25 and older who have CI on the Apsáalooke Reservation.

Primary hypothesis: Those AI adults on the Apsáalooke Reservation participating in the *Baa nnilah* intervention will have significant improvement in quality of life using the SF-12 measure compared to a wait-listed control group immediately following the intervention and at 6 and 12 months post-intervention.

[figure not shown]
Secondary hypothesis: Those AI adults on the Apsáalooke Reservation participating in the *Baa nnilah* intervention will have significant improvement in measures of satisfaction in and participation with social roles and activities, social isolation, patient activation, health care relationship, physical function, and depression compared to a wait-listed control group immediately following the intervention and at 6 and 12-months post-intervention. Our mixed-methods design includes a qualitative evaluation of fidelity and acceptability immediately post-intervention.

This study is considered a Phase 3 clinical trial. Please see the attached document, "Protection of Human Subjects" from our grant application that contains human subjects information (some overlap with what is below) and our Data Safety and Monitoring Plan, which is required for Phase 3 clinical trials. This clinical trial has been registered at Clinicaltrials.gov with the following NCT identifier: NCT03036189.

As this project takes place on a reservation, please see the attached letter of support/approval from the Crow Nation.

See picture below for a graphic depiction of our study design:

Research Design of the *Báa nnííłah* Program A Group Randomized Trial

B. RESEARCH PROCEDURES INVOLVED. Provide a short description of sequence and methods of procedures that will be performed with human subjects. Include details of painful or uncomfortable procedures, frequency of procedures, time involved, names of psychological tests, questionnaires, restrictions on usual life patterns, and follow up procedures

There are three different groups from whom data will be gathered. Answers to the questions below are grouped according to who is providing the information.

1. Participants of intervention: all participants
2. Participants of intervention: subgroup
3. Intervention facilitators

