1. Participants of intervention: all participants: 200 Crow community members will be recruited by other community members (described below under D5), provide informed consent (form attached), and be randomly assigned by family/friend cluster to an intervention or wait-list control group (both groups will receive the intervention). Random assignment will occur via cluster so that family members or friends who are interested in participating in the intervention together will remain in the same group. During the month of October 2017, groups of approximately 10 community members will attend an orientation and data collection session – this is the baseline data collection. The groups are based on the community in which they will attend the intervention meetings and include: Wyola, Lodge Grass, Crow Agency, Hardin, and Pryor, MT.

[figure not shown]
During the orientation/data collection session, participants will complete a survey and 3 exercises. All measures in the survey that are in an index form (one measure with multiple questions) come from the NIH PROMIS measure bank (<http://www.healthmeasures.net/index.php>), are other validated measures, or are demographic or fidelity measures used in other studies. All measures

are included with the application and begin with the page labeled "Measures". The survey responses and results of the exercises will be on a tablet computer and will look similar on the computers (the measures attached are in different formats at present).

[figure not shown]
The survey questions will be read out loud by a project staff member. Participants will be seated so that they do not see the responses being entered into other computer tablets by other participants. We are working with the MSU HELPS lab to facilitate data collection. Survey respondents will provide their responses on tablet computers using Qualtrics offline software and unique identification codes. Once a respondent has submitted the survey, those answers will not be viewable by subsequent research participants. The responses will upload to the secure Qualtrics servers once the tablets are again connected to a wi-fi network. Data will not be maintained on the tablet computers in the long term.

Three basic physical function tests will be performed: timed up and go (TUG), static balance assessment (BESS), and 6 minute walk. Brief descriptions of the tests are below. Responses will be entered into the computer tablets.

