12. During the past 4 weeks, how much of the time has your physical health or emotional problems interfered with your social activities (like visiting friends, relatives, etc.)?

1 All of the time 2 Most of the time 3 Some of the time 4 A little of the time 5 None of the time

Patient name: _____ Date: _____ PCS: _____ MCS: _____

Visit type (circle one)
Preop 6 week 3 month 6 month 12 month 24 month Other: _____

Physical Function – Short Form 8b**Please respond to each question or statement by marking one box per row.**

		Without any difficulty	With a little difficulty	With some difficulty	With much difficulty	Unable to do
PFA11	Are you able to do chores such as vacuuming or yard work?	 5	 4	 3	 2	 1
PFA21	Are you able to go up and down stairs at a normal pace?	 5	 4	 3	 2	 1
PFA23	Are you able to go for a walk of at least 15 minutes?	 5	 4	 3	 2	 1
PFA53	Are you able to run errands and shop?	 5	 4	 3	 2	 1
PFC12	Does your health now limit you in doing two hours of physical labor?	 5	 4	 3	 2	 1
PFB1	Does your health now limit you in doing moderate work around the house like vacuuming, sweeping floors or carrying in groceries?	 5	 4	 3	 2	 1
PFA5	Does your health now limit you in lifting or carrying groceries?	 5	 4	 3	 2	 1
PFA4	Does your health now limit you in doing heavy work around the house like scrubbing floors, or lifting or moving heavy furniture?	 5	 4	 3	 2	 1

Self-Efficacy for Managing Symptoms – Short Form 8a**Please respond to each question or statement by marking one box per row.**

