SSQ4x2	I have someone I trust to talk with about my problems	 1	 2	 3	 4	 5

Self-Efficacy for Managing Emotions – Short Form 8a**Please respond to each question or statement by marking one box per row.**

CURRENT level of confidence...					
	I am not at all confident	I am a little confident	I am somewhat confident	I am quite confident	I am very confident
SEMEM015 I can handle negative feelings.....	 1	 2	 3	 4	 5
SEMEM018 I can find ways to manage stress.....	 1	 2	 3	 4	 5
SEMEM016 I can handle upsetting situations	 1	 2	 3	 4	 5
SEMEM012 I can avoid feeling discouraged.....	 1	 2	 3	 4	 5
SEMEM017 I can keep emotional distress from interfering with things I want to do.....	 1	 2	 3	 4	 5
SEMEM010 I can bounce back from disappointment	 1	 2	 3	 4	 5
SEMEM003 I can relax my body to reduce my anxiety..	 1	 2	 3	 4	 5
SEMEM019 I can handle the stress of going for treatment of my medical conditions	 1	 2	 3	 4	 5

Positive Affect and Well-Being - Short Form

Please respond to each question or statement by marking one box per row.

Lately...		Never	Rarely	Sometimes	Often	Always
NQPPF14	I had a sense of well-being.....					
NQPPF12	I felt hopeful.....					
NQPPF15	My life was satisfying.....					
NQPPF20	My life had purpose.....					
NQPPF17	My life had meaning.....					

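### The SAP drops the protocol's outcome ranking and controls no error rate, so a chance result on any of 13 instruments beyond the SF-12 could be reported as a tested effect

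*SAP*

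**What the plan says.** The protocol (section VII.A, Aim 2) sets two tiers. The primary hypothesis is that participants "will have significant improvement in quality of life using the SF-12 measure compared to a wait-listed control group immediately following" the intervention and at two later times. A single secondary hypothesis covers six constructs: social roles and activities, then "social isolation, patient activation, health care relationship, physical function, and depression compared to a wait-listed control group". The protocol does not say which instrument represents each construct, and it gives no rule for error control.

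The instruments appear elsewhere in the protocol. Section VII.B, item 1 says: "Three basic physical function tests will be performed: timed up and go (TUG), static balance assessment (BESS), and 6 minute walk". The Measures section adds a fourth instrument for the same construct, "Physical Function – Short Form 8b". It also contains scales for matters that neither hypothesis names, such as "Self-Efficacy for Managing Symptoms – Short Form 8a" and "Self-Efficacy for Managing Emotions – Short Form 8a".

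The SAP (Statistical analysis) fits a hierarchical linear model "To test the main hypotheses regarding the effectiveness of the intervention and longitudinal trend on each outcome measure". The effectiveness question within that model is "whether the change significantly differed between the two study groups". The SAP contains no list of outcomes, no primary or secondary label, no alpha, no order of testing and no multiplicity adjustment.

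**The concern.** Under the SAP's wording, every outcome is tested for effectiveness on the same footing. A reader of the SAP cannot tell an outcome that the protocol hypothesised about from one that was simply collected. If a coping or self-efficacy scale shows p below 0.05, nothing in the SAP prevents that being reported as a tested effectiveness hypothesis. If one of the four physical-function measures does so, nothing prevents a claim that physical function improved, based on the best of the four.

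This matters because the protocol calls the study a Phase 3 trial (section VII.A and the data safety and monitoring plan). The SAP is also dated 8/23/22 and written in the past tense, after data collection. With no ranking in the SAP, a reader cannot exclude that emphasis among the outcomes was chosen once results were known.

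**Working it through.** **Step 1. Match the instruments to the hypotheses.** These are the instruments in the protocol other than the SF-12.

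| Instrument | Place in protocol | Construct in Aim 2 |
|---|---|---|
| TUG, BESS, 6-minute walk | VII.B, item 1 | physical function |
| Physical Function 8b | Measures | physical function |
| Satisfaction with Participation in Social Roles 8a | Measures | social roles |
| PAM-13 | Measures | patient activation |
| PHQ-9 | Measures | depression |
| Emotional Support 8a | Measures | arguable; nearest is social isolation |
| Self-efficacy for symptoms 8a, emotions 8a, social interactions 4a | Measures | none |
| COPE items | Measures | none |
| Positive Affect and Well-Being | Measures | none |

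Count: 3 + 1 + 1 + 1 + 1 + 1 + 3 + 1 + 1 = 13. Seven map to a named secondary construct, four of them to physical function. Five match nothing and one is arguable. COPE is counted as one score.

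**Step 2. Assumptions.** The documents give no alpha, no family-wise error rate and no correlation between outcomes, so there is no figure of the plan's own to reproduce. I assume two-sided 0.05 per test, one group contrast per instrument, no true effect, and a common correlation ρ between test statistics from 0 to 0.8.

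**Step 3. Independent tests.** The chance of at least one false positive among m tests is 1 − 0.95^m.

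- m = 13: 1 − 0.95^13 = 48.7%
- m = 7: 1 − 0.95^7 = 30.2%
- m = 4: 1 − 0.95^4 = 18.5%

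For the favourable direction only, replace 0.95 by 0.975. For m = 13, 1 − 0.975^13 = 28.0%.

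**Step 4. Correlated tests.** Write each statistic as Z = √ρ·U + √(1−ρ)·e, with U shared by all instruments. Then

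P(at least one) = 1 − ∫ [Φ((1.96 − √ρ·u)/√(1−ρ)) − Φ((−1.96 − √ρ·u)/√(1−ρ))]^m φ(u) du,

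evaluated by Gauss-Hermite quadrature. For the favourable direction, the second Φ term is dropped.

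| m | Direction | ρ = 0 | 0.3 | 0.5 | 0.7 | 0.8 |
|---|---|---|---|---|---|---|
| 13, all | either | 48.7% | 41.8% | 33.4% | 24.1% | 19.2% |
| 13, all | favourable | 28.0% | 21.4% | 16.7% | 12.0% | 9.6% |
| 7, mapped | either | 30.2% | 27.1% | 23.0% | 17.8% | 14.9% |
| 4, physical function | either | 18.5% | 17.4% | 15.6% | 13.0% | 11.4% |
| 4, physical function | favourable | 9.6% | 8.7% | 7.8% | 6.5% | 5.7% |

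**Step 5. Compare with a single test.** Across the 13, the either-direction rate is 19.2/5 = 3.8 to 48.7/5 = 9.7 times nominal. For physical function alone it is 11.4/5 = 2.3 to 18.5/5 = 3.7 times nominal. The inflation exceeds twofold at every correlation shown, so the conclusion does not depend on choosing 0.5.

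**Step 6. Sensitivity of the count.** Scoring COPE as two measures gives m = 14 and 34.8% at ρ = 0.5, so the count is not critical.

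**The case against.** The SAP is one short section. Its reference to main hypotheses follows a paragraph on descriptive and baseline comparisons, so it may simply mean the protocol's primary and secondary hypotheses. On that reading the ranking still stands in the protocol, and nothing shows that COPE or the self-efficacy scales were raised to equal status. The 13 instruments come from the 2017 measures, not from a list in the SAP. It is also common practice to leave secondary outcomes unadjusted.

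Part of this stands. A reader might infer that the plan has no tiers at all, but the protocol has them; the fault is that the SAP does not carry them over. That all 13 instruments were tested is an inference from the SAP's scope, which covers each outcome without listing any. It has some support, because the SAP's missing-data text mentions participants declining a physical test, which points to the performance tests being analysed. Unadjusted secondary outcomes are acceptable when labelled as such, and here they are not. Even on the narrow reading, physical function has four candidates, and no alpha is stated.

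Some stronger readings are tempting but unsupported:

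- A reader might attribute the 33% to the four physical-function measures. Those four give at most 18.5%; the 33% needs all 13 instruments and a correlation of about 0.5.
- A reader might conclude that a false claim of benefit is likely. With one contrast per instrument, the favourable-direction rate is 28% at most.
- A reader might multiply the tests by the protocol's three post-intervention times. The SAP models time continuously in weeks from baseline and specifies no separate tests at those times.
- A reader might infer that social isolation and health care relationship were never measured. The available text is incomplete, and the protocol's list under Sources of materials includes both.

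**Conclusion.** The concern holds as a matter of ranking and reporting. The SAP omits the protocol's primary and secondary tiers and sets no error control. The protocol names no deciding instrument for physical function, and at least five collected measures belong to no hypothesis.

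Under the assumptions in the working, none of which the documents state, the chance of at least one false positive in either direction among 13 instruments is about 33% (19% to 49% for correlations of 0.8 to 0). For a false finding of benefit it is about 17% (10% to 28%), against a nominal 2.5%. For the four physical-function measures alone it is about 16% (11% to 19%) in either direction.

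The protocol's choice of the SF-12 as primary is unaffected. What changes is which other results may be called evidence of effectiveness.

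**What to change.** In the SAP and the report, replace the uniform testing of all outcomes with the ranking in protocol section VII.A, Aim 2:

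- **Primary:** the SF-12.
- **Secondary:** the six named constructs, including social isolation and health care relationship wherever an instrument was administered.
- **Exploratory:** every other measure, reported with estimates and 95% confidence intervals and no effectiveness claim.

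For physical function, either name one deciding instrument with a reason that does not depend on the results, or report all four together and make no claim from the best one. The protocol does not settle which instrument decides, so the sponsor should make and justify that choice.

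State alpha. Then either adjust the named secondary constructs by Holm at an overall two-sided 0.05, or report them as unadjusted and supportive only. Making the secondary tests conditional on the SF-12 is optional. Because the SAP postdates data collection, say openly that the ranking is taken from the protocol's hypothesis wording.

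The cost is wording, plus a Holm adjustment of a few p-values if that option is chosen; no new data or models are needed. The downside is that an isolated secondary or exploratory result with p below 0.05 may no longer support an effectiveness claim. With six constructs, Holm's first threshold is 0.05/6 = 0.0083; with four it is 0.05/4 = 0.0125.

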Depending on the space available, this can be around the outside of a large room or could be back and forth in a hallway. A step counter is used to record the number of steps the individual takes in the six minutes. Distance walked can then be calculated based on the length of an individual step.

See the research design graphic above: Next, participants in the intervention group will attend the intervention.

The intervention consists of 7 group education sessions (called gatherings), conducted every other week in the local communities and led by community mentors. A manual for the mentors for the education sessions is being finalized at this time so that the sessions remain consistent across mentors and across the intervention and wait-list control groups; all mentors have been recruited and are meeting monthly with project staff to co-develop the intervention materials and receive training. Next, all 200 participants will attend another data collection session in their same groups in March 2018. Next, the waitlist control group will attend the 7 intervention sessions, which will be identical to the intervention group via the mentor manual. All 200 participants will provide outcome measures again in August 2018 and December 2018. The measures will be the same for each data gathering session with the exception of a few questions that will be asked after the intervention only (as noted in the attached measures handout) and are focused on measuring outcomes related to intervention content.

2. Participants of intervention: subgroup. A random sample of 20 participants will be selected – 10 from the intervention group and 10 from the wait-list control group. These participants will be invited to participate in a qualitative interview. [name], Co-PI of this grant will conduct the interviews, which are expected to last approximately one hour. The interview will be audio-taped and transcribed verbatim. Qualitative data analysis methods used in our prior studies will be conducted on this data. Participants will select a location to be interviewed where they are comfortable and where confidentiality will be assured. The questions for the qualitative interview are included with this application and are titled: “Báa nnilah program qualitative interview questions”

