- Since starting with the Báa nnilah program, what other support in addition to being in the program has made a difference for your health?
- In your observation, what changes have you noticed in the community as a result of this program?
- What do you see for yourself for the future?
 - What information/tips/techniques from the program will you use in the future?

- What ideas do you have for the future of the Ba nnilah program in the Crow community?

Aho. Thank you for your time today. You are helping us to make the Ba nnilah program most effective.

Facilitator measures of fidelity

1. Recruitment: Mentor will have a “Participant Notebook” where they keep track of names and contact information of community members they recruited, location of recruitment, and date of recruitment. We will also gather information on emergency contacts for each participant. We will use this notebook to track recruitment efforts. Note: The Participant Notebook will not be linked to the outcome data in order to protect confidentiality of participant information.
2. Entry into study: The Participant Notebook will also have information on the date the mentor consented the participant and the date they held a meeting with the participant to hear their health story.
3. Retention:
 - a. Each gathering will include a mentor check list of participant attendance, which the mentor will transfer into the Participant Notebook, which will be changed to number of gatherings attended by each participant in the database.
 - b. For gatherings missed by participants, the mentor will indicate if the participant provided a reason for missing the gathering
 - c. Participants who drop out of the study will be contacted by project staff (not the mentor who is leading their gatherings) and asked for their reasons for drop out.
4. Dose: Each gathering will include a mentor check list of which components of the gathering they facilitated and the length of the gathering in minutes. An example is included in the materials. The evaluation will consist of the number of manual-based intervention components delivered divided by the total number intended. The checklist also includes three questions:
 - a. How comfortable were you in leading this gathering?
Not at all comfortable to Very comfortable on a scale of 1-10
 - b. How confident were you in leading this gathering?
Not at all confident to Very confident on a scale of 1-10
 - c. Please share any comments you have about leading this gathering.

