Weather					
Lack of transportation					
My personal health					
Deaths in the community					
Death in the family					
Personal or family crisis					
Community events					
Work schedule					
Not being informed of gathering times and locations					
Changing schedule of gatherings					
Location of gatherings					
Family member care					
Atmosphere and feeling of gatherings					
-Please explain any gathering issues:					
Other (please explain):					

2. Participants of intervention: subgroup – no changes at this time

3. Intervention facilitators. We are adding a data collection element.

There are 10 intervention facilitators who are Crow community members. They are each leading 7 gatherings/meetings in the community. We are taking a random sample of one of the 10 facilitators for each of the 7 gatherings to complete an additional fidelity evaluation. The data will be gathered by co-PI [name], a member of the Crow Nation. The evaluation instrument is below.

In addition, for process evaluation and fidelity tracking, we are keeping field notes of texts and phone call communications with the intervention facilitators. This information will provide context and a deeper understanding of the delivery of the intervention. An example of this information is when a gathering is postponed due to weather or because participants are out of town at a basketball tournament.

6. Have these requested changes been initiated?

- No – for #1, participants of intervention
- Yes – for #3, intervention facilitators

7. How will the proposed modification(s) affect study participants?

Note: Federal regulations require IRB approval prior to changing a research procedure or deviating from IRB approved documents unless it is in the best interest of or for the safety of study participants.

The only affect is that the survey (#1 above) will take approximately 5 minutes longer for participants.

		Not Completed	Partially Completed	Fully Completed	Did the Mentor add new components not in the original protocol?
Welcoming, prayer, meal	30 min				
Story	10 min				
Mentor provides information: introduction/purpose of gathering	30 min				
Sharing circle	50 min				
Supportive partnerships activity	50 min				
Closing	10 min				
Mentor Responsibility (Communication with participants, bringing all necessary materials, being on-time, etc.)					
Mentor Interactional Style (Ex. Speaking Crow, facilitation style, food choices, humor, empathy, etc.)					
Comments:					

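### The effectiveness model adjusts for total gatherings attended, a post-randomisation count held fixed over all waves: its coefficient is not a dose-response, and it can lower the attended-sessions coefficient

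*SAP*

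**What the plan says.** The SAP (Statistical analysis) uses one mixed model per outcome to test the main hypotheses. Among its covariates: "Time-invariant covariates included age at baseline, sex, study group membership, number of chronic illnesses, and number of gatherings attended". The same model carries an exposure term that does change with time: "a dummy variable indicating whether each participant had attended intervention sessions at each time of data collection was included in the analytical model". The stated question is whether outcomes changed over time and "whether the change significantly differed between the two study groups", which I read as a group-by-time term. The SAP does not say which coefficient is the intervention effect, states no dose-response hypothesis, and reports no attendance distribution or intraclass correlation.

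The protocol (Facilitator measures of fidelity, item 3a) says that attendance is taken at each gathering, copied to the mentor's notebook, "which will be changed to number of gatherings attended by each participant in the database". One count per person, from 0 to 7, is therefore what reaches the analysis.

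On timing, section VII.B, item 1, places the second data collection after the intervention arm's sessions and before those of the wait-list arm: "Next, the waitlist control group will attend the 7 intervention sessions". The participant handout shows the same order.

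One amendment adds a survey list of things that kept people from attending. It includes "My personal health".

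**The concern.** Age and sex are fixed before randomisation. The number of gatherings attended is not: it is the dose received, and it builds up during follow-up. Treated as time-invariant, a wait-list member who eventually attends seven gatherings carries a seven at baseline and at wave 2, before attending any. An intervention member carries the final total at baseline.

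Two coefficients are at risk. The first belongs to the count. It compares people who chose to attend more with people who chose to attend less, and it averages over rows before and after the dose. If health affects attendance, as the survey item allows, it can be positive with no programme effect and be taken for dose-response. The second belongs to the attended-sessions indicator. Someone who never attends has zero on both terms at every wave, so a slope on the count inflated by selection is offset by a lower coefficient on the indicator. A useful programme could then look weaker than it is.

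**Working it through.** **Rows affected.** From the SAP: 104 intervention participants with up to 4 waves and 107 wait-list participants with up to 5.

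- All rows: 104 × 4 + 107 × 5 = 416 + 535 = 951.
- Rows before any session: 104 × 1 (baseline) + 107 × 2 (baseline, wave 2) = 104 + 214 = 318.
- Share: 318 / 951 = 33%.

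These are maxima, because waves were missed. They also assume the order in section VII.B. A later amendment moves the second data collection to April/May 2018 without restating the session months.

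**Simulation inputs.** The plan has no figure to reproduce, so sizes come from simulation. Sample sizes and waves are the SAP's. Everything else is assumed: within-person correlation about 0.6 or higher, about 20% never attending, attenders averaging about 5 of 7 gatherings, and a true effect of 0.05 SD per gathering (0.05 × 5 = 0.25 SD in attenders). Strong selection means that the log-odds of attending rise about 0.5 per SD of health, a health–attendance correlation of about 0.4. Moderate selection is about half that log-odds. The model has time, group, group-by-time and the attended indicator, fitted with and without the total.

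**Attended-sessions coefficient (SD).**

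| Selection | Without total | With total | Loss |
|---|---|---|---|
| None | 0.24 | 0.23 | 0.01 / 0.24 = 4% |
| Moderate | 0.24 | 0.18 | 0.06 / 0.24 = 25% |
| Strong | 0.24 | 0.13 | 0.11 / 0.24 = 46% |

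The group-by-time coefficient was the same with and without the total to within about 0.001.

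The shift is roughly additive rather than proportional. In one strong-selection set it was 0.24 − 0.11 = 0.13 SD with a true effect and 0.02 − (−0.09) = 0.11 SD with none. The percentage therefore depends on the assumed effect: at 0.10 SD per gathering, strong selection moved the coefficient from 0.445 to 0.347, a loss of 0.098 / 0.445 = 22%.

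Fewer never-attenders also shrink it. In a further strong-selection variant, where the coefficient without the total was 0.22, it fell to 0.13 with 10% never attending and to 0.18 with 2%.

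**Population calculation without selection.** With an effect linear in dose and 5–30% never attending, the attended coefficient keeps 0.87 to 0.97 of its true value at an intraclass correlation of 0.5, and 0.93 to 0.98 at 0.7. It keeps all of it if everyone attends at least once.

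**Coefficient on the total.** With no programme effect and selective attendance, the least-squares simulations gave about +0.08 to +0.25 SD per gathering, depending on the strength of selection. A separate set of maximum-likelihood mixed-model fits (person correlation 0.55, about 20% of follow-up waves missed) gave a smaller coefficient, +0.06. It was nonetheless significant in 71% of runs, against 5% without selection. In the same set, with no selection and a true slope of 0.06 per gathering, the time-invariant total estimated 0.016 and the count by wave 0.063.

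**Effect of recoding.** Using gatherings attended by each wave cut the false-positive rate from 71% to 36%. It did not remove it.

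**The case against.** The best defence has four parts.

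1. The attended-sessions coefficient is estimated largely from within-person change, which a time-invariant term cannot absorb. This stands where attendance is unrelated to health.
2. The SAP's stated test concerns the difference in change between groups, and that term hardly moves. This stands in full.
3. The evidence for selection is one of 13 named barriers in a survey, beside weather, transport and bereavement. It is a question, not a result. This stands: selection is plausible but not shown.
4. Adjusting for attendance may remove some confounding. This stands in part. When attendance followed stable health only, the attended coefficient was 0.27 without the total, somewhat too high, and 0.17 with it, too low.

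Three stronger readings are tempting and are not supported.

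- A reader might infer that the covariate roughly halves the estimated effect of attending. One variant does give 0.22 falling to 0.11. It needs strong selection together with about a fifth never attending, and the documents give neither.
- A reader might blame a false dose-response on the time-invariant coding. It comes mainly from selection. The coding distorts a true slope.
- A reader might infer from item 3a that dose by wave is lost. In the planned schedule each arm's seven gatherings fall between two consecutive waves, so dose by wave follows from the total.

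What survives is that a post-randomisation count sits in the effectiveness model with no stated purpose, and that two of the model's coefficients depend on it.

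**Conclusion.** The point holds and should be fixed; it is not a fatal flaw. The SAP conditions its effectiveness model on a post-randomisation total that predates the dose on up to a third of rows. That much follows from the documents without assumptions beyond the session order.

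The total's coefficient should not be interpreted as dose-response under any of the scenarios examined. The SAP states no such hypothesis, so misreading is a risk rather than a declared intention. The downward bias in the attended-sessions coefficient runs from almost nothing to about 45%. Its place in that range depends on how strongly attendance follows health, how many never attended, the within-person correlation and the true effect, none of which is reported. The group-by-time comparison is essentially untouched, so a conclusion resting on that term is not threatened by this covariate.

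**What to change.** Delete number of gatherings attended from the covariates of the effectiveness model and re-run it.

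If dose is of interest, fit a separate model labelled exploratory. Replace the fixed total with gatherings attended by each wave: 0 before the arm's session window and the total afterwards. This gives 0 at baseline for everyone and 0 at wave 2 for the wait-list arm. State beside the result that selective attendance can still produce a false dose-response.

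The variable can be built from the total already held. No database change is needed, and the mentor notebooks, which the protocol keeps unlinked from outcome data, need not be opened. Because the amendment moved the data-collection months, confirm first that each wait-list group's wave 2 came before its first gathering.

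It would also help to report the attendance distribution by arm, including how many attended none, so that readers can judge where in the range this trial falls.

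The cost is one deleted covariate, one recoded variable and a re-run of existing models. The downside is that the attendance coefficient no longer appears in the main table. Deleting it does not make the attended-sessions indicator a randomised contrast, because that term also depends on who chose to attend.
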